4.6.2 Data Collection and Follow-up for Withdrawn Subjects

Follow-up data will be collected at 12 months on the subjects who withdraw from the study after obtaining the subject's permission to record this information.

Lost-to-follow-up

692

693

694

695 696

697

698

699

700

701 702 703

704

705

706

707

708 709

710

711 712

714

716

717 718

719

720

721

722 723

724

725 726

727 728

730 731

732

734

735

• A minimum of 2 phone calls and 1 certified letter contact attempts will be made before a patient is considered as a lost-to-follow-up.

713 5 Study Drug

5.1 Description

- 715 Saxenda® or matching placebo
 - Subcutaneous Solution: 6 mg/ml
 - Solution for subcutaneous injection, pre-filled, multi-dose pen that delivers doses of 0.6mg, 1.2 mg, 1.8 mg, 2.4 mg or 3.0 mg (6mg/mL, 3mL)

5.2 Treatment Regimen

Dose:

- Recommended dose of Saxenda® or matching placebo is 3.0 mg daily
- Administer at any time of the day, without regard to the timing of meals

Dose escalation should be used to reduce the likelihood of GI symptoms

- **Week 1:** 0.6mg/day
 - Week 2: 1.2mg/day
- Week 3: 1.8mg/day
- Week 4: 2.4mg/day
- Week 5 and Onward: 3.0mg/day
 - May delay dose escalation for 1 additional week if unable to tolerate increased dose
 - Discontinue if patient is unable to tolerate the study drug for any reason

733 Route:

- Inject subcutaneously in the abdomen, thigh or upper arm.
- The injection site and timing can be changed without dose adjustment.

5.3 Subject Compliance Monitoring

- The study drug will be dispensed to each subject at study visits (baseline, 3, 6, 9 months) and will be recorded by the investigational pharmacy and study team.
 - The subjects are required to return used pens when receiving new drug and the number of used pens returned will be recorded by the investigational pharmacy.
 - Subjects are required to bring a daily study drug administration log to 3, 6, 9, and 12 months study visits.
 - Subjects who are not compliant with administrating the study drug ≥ 30 days will be withdrawn from the study.

5.4 Concomitant Therapy

Avoid use with insulin

736

739

740

741

742

743

744

745

746

747

750

751

752 753

754 755

756

757

758

759

760

761

762

763

764

765

766

767

769

770

771

- Avoid use with other glucagon-like peptide-1 receptor agonists
- Advise to take daily post RYGB supplements which include multivitamin with copper, calcium, vitamin D, iron, and vitamin B12.

5.5 Receiving, Storage, Dispensing and Return

5.5.1 Receipt of Drug Supplies

- Upon receipt of the study treatment supplies, an inventory will be performed and a drug receipt log filled out and signed by the person accepting the shipment.
- The designated study staff will counts and verifies that the shipment contains all the items noted in the shipment inventory.
- Any damaged or unusable study drug in a given shipment (active drug or comparator) will be documented in the study files.
- The investigator will notify Novo Nordisk of any damaged or unusable study drug that was supplied to the investigator's site.

5.5.2 Storage

- All study drugs will be stored at the NYULMC investigational pharmacy and distributed by the NYULMC investigational pharmacist.
- Store unopened prefilled pens refrigerated, between 2 and 8 degrees C (36 and 46 degrees F).
- Store opened pens up to 30 days at controlled room temperature, between 15 and 30 degrees C (59 and 86 degrees F), or refrigerated, between 2 and 8 degrees C (36 and 46 degrees F) and protect from excessive heat and sunlight.
- Avoid storing directly adjacent to cooling compartment in refrigerator.
- Do not freeze or use a pen that has been frozen.

5.6 Method for Assigning Subjects to Treatment Groups and Dispensing of Study Drug

5.6.1 Randomization Process

- Eligible subjects will be randomized to one of the two treatment groups in a 2:1 ratio to receive either
- study drug (Liraglutide (rDNA origin) injection, 3 x Saxenda® pen, NDC 0169-2800-13) or matching
- placebo, with stratification by gender and percent post-operative TBWL (<25%, 25 49.9%). Stratified
- block randomization will be employed. Randomization lists will be sent to the pharmacist who will then
- be able to distribute the study drug/placebo as patients are enrolled, and the remainder of the study staff

will be blinded.

5.6.2 Dispensing of Study Drug

778

782

786

787

788 789

790

791

792

The study drug will be dispensed to each subject at study visits (baseline, 3, 6, 9 months) upon returning the used pens and the compliance with study drug administration will be recorded by the investigational pharmacy and study team.

Study drug reconciliation will be performed to document drug assigned, drug consumed, and drug remaining. This reconciliation will be logged on the drug reconciliation form, and signed and dated by the study team.

5.6.3 Return or Destruction of Study Drug

At the completion of the study, there will be a final reconciliation of drug shipped, drug consumed, and drug remaining. This reconciliation will be logged on the drug reconciliation form, signed and dated. Any discrepancies noted will be investigated, resolved, and documented prior to return or destruction of unused study drug. Drug destroyed on site will be documented in the study files.

6 Study Procedures

Visit Number	1			2			3			4			5
	Baseline	1M	2M	3 months	4M	5M	6 months	7M	8M	9 months	10M	11M	12 months
Visit window	0-4 wks prior to the treatment			± 4 wks			± 4 wks			± 4 wks			± 4 wks
Informed consent	X												
Screening	X												
Demographics	X												
Medical History	X												
Weight, BP, HR, Waist & Neck Circumference	X			X			X			X			X
Height	X												
Medications	X			X			X			X			X
Blood Pregnancy Test (Beta Quantitative HCG) (Only applicable for women of childbearing potential)	X			X			X			X			X
¹ BMP, HbA1c, ¹ Lipid profile, Amylase, Lipase	X			X			X			X			X
Additional plasma and	X						X						X

serum for future analyses													
PHQ-9, IPAQ, 24 hr diet recall	X			X			X			X			X
Diet and Physical Activity Counseling by RD	X			X			X			X			X
Body Composition	X			X			X			X			X
Comorbidities: Diabetes, Hypertension, STOP-BANG	X			X			X			X			X
² AEs	X	X	X	X	X	X	X	X	X	X	X	X	X
Study Medication Compliance Phone call		X	X		X	X		X	X		X	X	

795

796

804

807

810 811

- 1. Fasting is required
- 2. Ask about hypoglycemia symptoms for patients with Type 2 DM

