
516517

We hypothesize that the liraglutide group will demonstrate greater improvement

in cardiovascular risk profile (as assessed by serum lipids, HbA1c, and waist

518	circumference) and quality of life (as assessed by the PHQ-9) at 12 months, than
519	the placebo group.
520	 To evaluate the safety of liraglutide in post-RYGB subjects.
521	o We will monitor adverse events, blood counts and serum chemistries in subjects
522	receiving liraglutide or placebo over a period of 12 months.
523	We hypothesize that the liraglutide group will exhibit more frequent
524	hypoglycemia and elevations in lipase and amylase, but that these episodes will
525	be clinically insignificant.
526	• To evaluate the changes in obesity-related comorbid conditions in patients who are experiencing
527	weight regain following RYGB.
528	 We will monitor obesity-related comorbid conditions in subjects receiving liraglutide or
529	placebo over a period of 12 months.
530	 We hypothesize that the liraglutide group will exhibit improvements in obesity-
531	related comorbid conditions (hyperglycemia, hyperlipidemia, blood pressure, and
532	obstructive sleep apnea) at 12 months, than the placebo group.
533	3.2 Endpoints
534	• Primary Endpoint: Proportion of subjects losing at least 5% of enrollment body weight at 12 months.
535	• Secondary Endpoints: Fasting serum glucose, HbA1c, LDL-cholesterol, HDL-cholesterol,
536	triglycerides, waist circumference, blood pressure, STOP-BANG score, PHQ-9
37	• Primary and secondary endpoints will be assessed at clinic visits prior to randomization and at 3, 6, 9
538	and 12 months post-first study drug administration.
539	3.3 Study Type
540	Randomized, single-center, double-blind, placebo-controlled study with two arms. Randomization will
541	be 2:1 (drug:placebo) with stratification by gender and percent post-operative TBWL (25%, 25 – 49.9%).
542	3.4 Rationale for study Design
543	A randomized, placebo-controlled study design was chosen as this is the methodology that will best
544	assess the efficacy of liraglutide for weight loss in the post-RYGB population. 2:1 randomization was
545 546	chosen with the intention of increasing potential participant interest given better than even odds of
547	randomization to liraglutide.
548	A single-center study was chosen given that the NYU Langone weight management program has a pool
549	of 700 post-RYGB patients in our retrospective database, and that recent data from our program suggests

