550	that 80 % of patients at least 18 months status-post RYGB exhibit regain of ≥10% of maximum post-
551	surgical TBWL – our program has a potential subject pool of 560. We estimate that at least 50% of 560
552	will be eligible for and agree to participate in the study, which will allow us to be able to enroll adequate
553 554	subjects from our program alone. In addition, approximately five post-RYGB patients are referred to our program monthly for evaluation of weight regain. In the case that subject recruitment falls short of goals,
555	we would expand recruitment using advertisements.
556	3.5 Primary Study Endpoints
557	Proportion of subjects losing at least 5% of enrollment body weight at 12 months.
	-r

Universal Trial Number: U1111-1178-7319 Version 7: 10/11/2019 Page 15

557

558	3.6 Secondary Study Endpoints
559 560 561	Fasting serum glucose, HbA1c, LDL-cholesterol, HDL-cholesterol, triglycerides, waist circumference, blood pressure, STOP-BANG score, PHQ-9, Obesity-related co-morbidities assessment
562 563	Primary and secondary endpoints will be assessed prior to randomization and at clinic visits at 3, 6, 9 and 12 months post-first treatment administration.
564	3.7 Primary Safety Endpoints
565 566	The primary safety endpoint is the percentage of patients who are experiencing AEs during 12 months of the trial.
567 568 569 570 571 572 573 574	 3.7.1 Assessments for Safety BMP (Fasting glucose) Amylase Lipase Pregnancy Test (Only applicable for women of childbearing potential) Heart Rate PHQ-9 Current medication list review
575	• Adverse event assessment including symptomatic hypoglycaemia for Type 2 DM patients
576	4 Subject Selection and Withdrawal
577 578	4.1 Number of the subjects: 132 Subjects will not be replaced if they withdraw or become ineligible.

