579 580 581 582 583 584 585 586 587 588	4.2 Rationale for study population The Roux-en-Y gastric bypass (RYGB) is not only the most common bariatric procedure, but also the gold standard to which all others are compared. The average weight loss after RYGB is approximately 35% total body weight. However, the majority of patients who undergo this procedure experience weight regain and thus are at risk of, or re-acquire co-morbid conditions, such as Type 2 diabetes mellitus or hypertension. Revisional surgery, which is the most common treatment for weight regain after bariatric surgery, is often thwarted by resistance from insurance companies, leaving patients with only diet and behavioral change as an option. Due to the fact the GLP-1 agonism plays a significant role in weight loss after RYGB, liraglutide is thought to be a promising adjunct to the long-term treatment plan in patients who experience weight regain after RYGB.
589	4.3 Inclusion Criteria
590 591 592 593 594 595 596	 >18 years who are deemed medically stable ≥18 months status-post RYGB at time of enrollment BMI of ≥30 kg/m² or ≥ 27 kg/m² in the presence of at least one weight-related comorbid condition Regain of ≥10% of maximum TBWL post-RYGB Ability to provide informed consent before any trial-related activities Express willingness to provide signed informed consent and follow protocol requirements
597	4.4 Exclusion Criteria
598	• BMI of $>45 \text{ kg/m}^2$

• Pregnancy at time of enrollment

600

604

605 606

607

608

609

610

613

614

622

623

624

625

626 627

628

629 630

631

632 633

634

635 636

637

638

639

640 641

642

643

644

645

- Intention of becoming pregnant or breast feeding in the next 12 months
- Females of childbearing potential who are not using adequate contraceptive methods
- Presence of acute psychiatric problems or immaturity which would compromise cooperation with the study protocol
 - Presence of biliary disease
 - Known or suspected allergy to liraglutide or any product components
 - Personal or family history of medullary thyroid carcinoma or multiple endocrine neoplasia syndrome type 2
 - History of pancreatitis
 - History of alcoholism
 - History of Type 1 DM (Diabetes Mellitus)
- History of previous bariatric surgery other than RYGB except h/o LAGB and band removal.
- >10 years status-post RYGB
 - < 25% TBWL at post-RYGB weight nadir
 - >50% post-operative TBWL at time of screening
- Simultaneous use of any weight loss medications

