1048			
1049		a contact with the subject, the investigator must seek information on adverse events by specific	
1050		ning and, as appropriate, by examination. Information on all adverse events should be recorded	
1051		iately in the source document, and also in the appropriate adverse event module of the case report	
1052	Torm (CRF) All clearly related signs, symptoms, and abnormal diagnostic procedures results should	

treatment follow-up is defined as 30 days following the last administration of study treatment.

The study period during which adverse events must be reported is normally defined as the period from the

initiation of any study procedures to the end of the study treatment follow-up. For this study, the study

recorded in the source document, though should be grouped under one diagnosis.

1053 1054 1055

1056

- 1059 All adverse events occurring during the study period must be recorded. The clinical course of each event
- 1060 should be followed until resolution, stabilization, or until it has been determined that the study treatment
- 1061 or participation is not the cause. Serious adverse events that are still ongoing at the end of the study
- period must be followed up to determine the final outcome. Any serious adverse event that occurs after 1062
- the study period and is considered to be possibly related to the study treatment or study participation 1063
- 1064 should be recorded and reported immediately.

1065 **8.2.1.1** Preexisting Condition

- 1066 A preexisting condition is one that is present at the screening of the study. A preexisting condition should
- be recorded as an adverse event if the frequency, intensity, or the character of the condition worsens 1067
- 1068 during the study period.

1069 8.2.1.2 General Physical Examination Findings

- 1070 At screening, any clinically significant abnormality should be recorded as a preexisting condition. At the
- end of the study, any new clinically significant findings/abnormalities that meet the definition of an 1071
- 1072 adverse event must also be recorded and documented as an adverse event.

1073 **8.2.1.3** Abnormal Laboratory Values

- 1074 A clinical laboratory abnormality should be documented as an adverse event if any one of the following 1075 conditions is met:
 - The laboratory abnormality is not otherwise refuted by a repeat test to confirm the abnormality
 - The abnormality suggests a disease and/or organ toxicity

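### A hypoglycaemia symptom question is documented only for subjects with type 2 diabetes, although the safety hypothesis covers all post-RYGB subjects

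*Combined protocol and SAP*

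**What the plan says.** **Who is asked.** Footnote 2 is attached to the adverse-event row of the schedule in section 6 and again in Attachment 1: "Ask about hypoglycemia symptoms for patients with Type 2 DM". Section 3.7.1 lists "Adverse event assessment including symptomatic hypoglycaemia for Type 2 DM patients".

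**What the safety aim covers.** Section 3.1 states the aim as "To evaluate the safety of liraglutide in post-RYGB subjects". The method is "We will monitor adverse events, blood counts and serum chemistries in subjects" on either treatment over 12 months. The hypothesis is that liraglutide will show more frequent "hypoglycemia and elevations in lipase and amylase, but that these episodes will" prove clinically unimportant. Nothing there limits it to subjects with diabetes.

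**Who can enter.** Section 4.3 admits subjects on BMI alone (30 or more), or on BMI of 27 or more "in the presence of at least one weight-related comorbid condition". Type 2 diabetes is neither required nor excluded.

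**What everyone receives.** Section 8.2.1 says that at contacts "the investigator must seek information on adverse events by specific" questioning. Section 6.2.7 adds a call or email to every subject in the eight months without a visit, to review compliance and adverse events. Fasting glucose is drawn from all subjects at every clinic visit (sections 1.6.1 and 6).

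**What is analysed.** Section 3.7 says "The primary safety endpoint is the percentage of patients who are experiencing AEs during 12 months of" the trial. Section 7.2 plans no analysis of hypoglycaemia as such.

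**The concern.** The hypothesis concerns the whole trial population, but the event is looked for more closely in one subgroup. If staff follow the footnote as written, a subject with type 2 diabetes is asked about hypoglycaemia symptoms by name, while another subject has to volunteer them in answer to a general adverse-event enquiry.

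A low count among subjects without diabetes could then mean that episodes were rare or that few were elicited, and the data could not separate the two. This matters because section 1.1 says that safety in this population still has to be established, and because section 3.1 makes a claim about clinical importance. A fasting sample taken at a visit cannot settle that claim for symptoms felt on other days.

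**Working it through.** No figure in the plan depends on this point, so the check sets the sections side by side and counts contacts.

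**1. Contacts after baseline** (section 6 schedule and section 6.2.7)
- Clinic visits: months 3, 6, 9, 12 = 4.
- Monthly contacts: months 1, 2, 4, 5, 7, 8, 10, 11 = 8.
- Total: 4 + 8 = 12.

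**2. What is documented at those contacts**

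| Item | Type 2 diabetes | No diabetes |
|---|---|---|
| General adverse-event questioning | 12 contacts | 12 contacts |
| Fasting glucose | 4 visits | 4 visits |
| Named hypoglycaemia symptom item | yes, on the adverse-event row | none documented |

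Only the last row differs. The counts describe opportunities to record an event. They do not measure events missed.

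**3. Does another provision supply the named item for subjects without diabetes?**
- Section 8.2.1 requires specific questioning of everyone but does not name hypoglycaemia.
- Section 6.2.7 calls for a general adverse-event review.
- Section 1.6.1 gives an instruction to report hypoglycaemia symptoms, addressed to users of an insulin secretagogue.
- The fasting glucose threshold in section 1.6.1 (70 or below) triggers action for secretagogue users. It does not define an event for analysis.
- Section 8.2.1.3 lets an abnormal glucose value be recorded as an adverse event, but only where a sample was taken.

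None of these closes the gap for symptoms between visits.

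**4. Direction of the effect.** Among subjects without diabetes, let c be the fraction of true cases that are recorded, and let pL and pP be the true proportions with an event on liraglutide and placebo. With the same rule and intact blinding, c is the same in both arms:
- recorded proportions are c × pL and c × pP;
- recorded difference = c × (pL − pP), which is smaller than the true difference when c is below 1;
- recorded ratio = (c × pL) / (c × pP) = pL / pP, which is unchanged.

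So in this subgroup absolute rates and differences may be understated, but the direction of the comparison between arms is kept. What is distorted is the comparison of subjects with diabetes against subjects without.

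**5. Size.** This would need c, the share of subjects without diabetes and their event rate. The documents give none of these. The only rate stated is 23.0%, for type 2 diabetes (sections 1.6.1 and 8.1.2.1). The loss therefore cannot be estimated.

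**The case against.** The strongest reply has three parts.

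**The hypothesis may be a laboratory one.** It groups hypoglycaemia with lipase and amylase, and glucose is measured in every subject. This is not persuasive. Section 3.1 speaks of episodes, judges their clinical importance, and names adverse events among the things monitored.

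**General questioning already covers symptoms.** Section 8.1.2 counts any symptom as an adverse event, section 8.2.1 requires specific questioning, and section 6.2.7 reaches every subject between visits. The footnote adds an item for one group and does not forbid asking others. This stands. A reader might infer that subjects without diabetes are never asked about hypoglycaemia, but the documents do not support that. The adverse-event module of the case report form is not included, so the defensible statement is that no dedicated item is documented for them.

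**Targeting follows the known risk.** The only expected rate is for type 2 diabetes, and section 8.1.4.1 ties the serious risk to anti-diabetic therapy. That explains why the item exists for that group. It does not show that the others can be left to general questioning: section 1.2.10 lists hypoglycaemia among common reactions without limiting it to diabetes, and no rate is given for subjects without it.

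**Conclusion.** The point holds in a limited form. Three places in the protocol direct a hypoglycaemia symptom item to subjects with type 2 diabetes, while the section 3.1 hypothesis covers everyone. Symptomatic episodes between visits may therefore be less completely recorded in subjects without diabetes. This rests on staff applying the footnote as written and on the case report form having no universal hypoglycaemia item.

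Two stronger readings are tempting and should be resisted.
- **Bias between arms.** Diabetes is not a stratification factor, so a reader might infer an unfair comparison. The rule is the same in both randomised, blinded arms, so no systematic difference between them follows.
- **A measurable loss.** A reader might turn the contact counts, or the spacing of glucose samples, into a share of events missed. Those describe contacts and sampling, not symptomatic events.

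The weight is low. Hypoglycaemia is not a named endpoint and section 7.2 tests nothing on it. The primary safety endpoint counts any adverse event, so a subject with another event is counted already. Only the section 3.1 safety hypothesis is affected.

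**What to change.** Low priority, but cheap:

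1. Reword footnote 2 in section 6 and in Attachment 1, and the matching line in section 3.7.1, so that every subject is asked the same hypoglycaemia symptom question at each visit and monthly contact.
2. Before unblinding, fix what counts as a hypoglycaemia event for analysis: symptoms, a glucose value, or both.
3. Report the proportion of subjects with at least one event by arm, overall and by diabetes status.
4. Flag contacts made before and after the change.

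**Cost.** One extra question at contacts already scheduled, three wording changes and one definition. More minor or non-specific events will be recorded.

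Timing is the larger drawback. The text is Version 7, dated 10/11/2019, in a study planned for March 2017 to December 2020. That is about 31 of 46 months, or roughly two-thirds of the calendar. A change at that stage mixes two ways of asking within subjects already in follow-up, which is why the flag is needed. If the team prefers to leave the question alone, steps 2 and 3 can still be done without any new data collection, and the report should state that ascertainment differed by diabetes status.
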